**I. Background and Rationale**

Multiple Sclerosis (MS) is a chronic, progressive inflammatory disorder of the central nervous system. It is caused by loss of myelin, the outer protective layer of the neuron, resulting in a disruption of the signal potentials that flow through the neurons. This can lead to a variety of sensory, visual, and motor disturbances. Demyelinated lesions eventually affect the myelinated nerve tracts that mediate lower urinary tract dysfunction. MS affects almost 1 million people in the United States with the prevalence being two to three times higher in women than in men. Over 80% of MS patients suffer from lower urinary tract symptoms, with bladder overactivity (OAB) and urinary incontinence (UI) being the predominant bladder dysfunctions. OAB is characterized by sudden feeling of urgency, frequent urination, and urge incontinence. Bladder conditions such as OAB have a negative impact on health-related quality of life, and OAB patients have more anxiety and depression than controls. In addition, MS patients with bladder dysfunction are at higher risk for future institutionalization, thus treatments are needed to improve bladder function. MS patients often utilize behavioral and fluid modifications and medications, with a subset progressing to minimally invasive overactive bladder third line therapies, including chemodenervation of the bladder with onabotulinumtoxinA (BTX), PTNS and sacral neuromodulation (SNM). Patient satisfaction and symptomatic improvement are high with all three therapies. Subtle patient characteristics and expectations make one treatment a "better choice" than another. Botox is the only FDA approved treatment, specifically studied to treat neurogenic urgency/ UUI. Percutaneous Tibial Nerve Stimulation (PTNS) is delivered by a slim needle that is placed in the ankle where the tibial nerve is located. When the tibial nerve is stimulated, impulses travel to the nerve roots in the spine to block abnormal signals from the bladder. We propose that the same mechanism that is effective for patients with OAB will be effective in the MS population that also suffers from OAB. PTNS is an FDA approved treatment for OAB and is recommended as third line treatment for OAB by the American Urological Association (AUA) and Society of Urodynamics, Female Pelvic Medicine and Urogenital Reconstruction (SUFU). However, it is not approved for MS and as such these treatments are not covered by insurance. The overall objective success (defined as >50% decrease in urge or urge urinary incontinence (UI) and 25% reduction in daytime and/or nighttime frequency) of PTNS for OAB has been published and ranges from 60% to 71%. The use of PTNS in the neuromodulation of MS-related OAB has only been explored in small case studies, but has demonstrated safety and efficacy. This has limited its inclusion in expert panel consensus recommendations and has prevented FDA approval for the use of PTNS in MS patients with OAB.

Here we propose a pilot, single blind, randomized, sham-controlled trial to assess the benefit of PTNS in treating OAB symptoms in MS patients. The data generated by this study would

Percutaneous Tibial Nerve Stimulation (PTNS) therapy for female patients suffering from  
Multiple Sclerosis

provide support for a future multi-institutional, randomized prospective trial. This would be essential for PTNS to gain FDA approval for its use in MS patients, increasing options for durable and cost-effective treatment of neurogenic urinary dysfunction.

## II. Objectives and/or Endpoints

The objective of this pilot study is to determine if PTNS therapy improves OAB symptoms in MS patients. We hypothesize that PTNS will significantly improve OAB symptoms in MS patients. We aim at using both subjective and objective measures to measure change in symptom severity (e.g. decrease in urinary frequency, urgency and incontinence).

The **primary outcome measure** will be assessed using the PGI-I, a self-reported measure of symptom improvement after treatment completion. This is a validated 1-question tool to which patients score their urinary tract condition now as compared to how it was before starting treatment. The score ranges from 1-7, with 1 being very much better and 7 being very much worse. The **secondary outcome measures** will determine change in urinary symptoms including frequency, urgency, and urinary incontinence, using a 3-day voiding diary, and measure quality of life parameters based on OAB symptoms, using the OAB quality of life short form questionnaire (OABq-SF). All questionnaires are grade A survey tools standardly used for the subjective and objective assessment of OAB symptom and symptom bother. PGI-I questionnaire will be completed at end of 4, 8 and 12 treatments, as well as at follow-up visit (Visit 13), as it is a score of self-reported symptom improvement. Secondary outcome measures will be assessed at baseline (prior to visit 1) and at the end of treatment (visit 13). Unlike idiopathic OAB, OAB symptoms in MS do vary typically in relationship to the disease process, thus closer intervals of assessing change are necessary.

**Primary (or general) objectives:** Assess the impact of PTNS therapy in female MS patients on subject-reported symptom improvement using the Patient Global Impression of Improvement (PGI-I) score.

**Secondary (or specific) objectives:** Determine the subjective and objective change in OAB symptoms in response to PTNS therapy using the OABq-SF and 3-day voiding diary.

## II. Methodology

This is a pilot, single blind, sham-controlled randomized trial. Female MS patients will be recruited by [name] of the Neurology department and by [name] of the PM&R department, as well as private Urology offices. They will be screened by the research nurse coordinator according to the specific inclusion and exclusion criteria.

We anticipate enrolling 34 patients, in this randomized trial, 17 in each study arm. Eligible participants will be consented and randomized into 1 of 2 groups. Patients will be enrolled in the study and randomized:

- After all screening activities have occurred and it has been determined that the patient meets all inclusion criteria without the presence of exclusionary criteria.

Percutaneous Tibial Nerve Stimulation (PTNS) therapy for female patients suffering from  
Multiple Sclerosis

- After the patient agrees to enroll and comply with the study protocol, regardless of study group assignment.

Patients will be randomized 1:1 to active PTNS treatment or Sham treatment.

The process of randomization will be as follows:

Randomization will be performed using a table of random numbers. Randomization envelopes will be provided by the study's biostatistician. Randomization assignment will be to either active PTNS treatment or Sham treatment. The randomization envelopes will be securely stored in a locked cabinet. The Research Coordinator(s) will ultimately be responsible for maintaining the confidentiality and security of the randomization envelopes. The biostatistician will prepare more envelopes, if necessary. After the participant is randomized, staff will complete the **Subject Enrollment and Randomization Log**. The log may be stored in the locked cabinet with the envelopes. Ultimately the log will be stored in the regulatory binder.

[figure not shown]
All patients who enroll will be seen and treated at the Beaumont Urology clinical research suite.

**A. Study Intervention:**

**PTNS treatment:**

Patients will be placed in a comfortable position, sitting or supine. The treatment leg will be propped up comfortably on a footrest but draped and out of view from the patient. A 34-gauge needle electrode will be inserted at a 60-degree angle 5 cm cephalad to the medial malleolus and slightly posterior to the tibia (Fig. 1A). A PTNS surface electrode will be placed on the ipsilateral calcaneus as well as 2 inactive sham surface electrodes, 1 under the little toe and 1 on the top of the foot. When the PTNS lead set is connected to the Urgent PC stimulator, a current level of 0.5 to 9 mA at 20 Hz is selected based on each patient's foot and plantar motor and sensory responses. Treatment lasts 30 minutes and given once weekly for 12 consecutive weeks.

Figure 1: (A) PTNS and (B) Sham Treatment Configurations

**Sham treatment:**

Sham treatment has been previously optimized by our group. Since patients in the active arm will feel foot stimulation, the sham arm will mimic this feeling without the tibial nerve being stimulated. These patients will be positioned similarly as PTNS patients. The medial aspect of the lower extremity will be palpated and the tibial nerve site will be identified approximately 5 cm cephalad from the medial malleolus. A Streitberger needle will be used at the tibial nerve insertion site to simulate needle placement (Fig. 1B). Without puncturing the skin and secured in place with tape. The needle is not connected to any active electrodes, and will not provide any conductive transcutaneous nerve stimulation. Three electrodes will be placed on the patient's foot, two active TENS electrodes and one inactive TENS electrode. The TENS "grounding pad" will be a gel electrode pad from a TENS unit device that is placed on the bottom

**Percutaneous Tibial Nerve Stimulation (PTNS) therapy for female patients suffering from  
Multiple Sclerosis**

of the foot just below the smallest toe. Another gel electrode will be placed on the top of the foot just above the small toe for conduction. These two electrodes will be connected to the TENS unit lead wires for sham stimulation. A third, inactive, gel electrode, will be placed near the medial aspect of the calcaneus to mimic the PTNS treatment. All TENS electrodes are reusable and may be designated for individual patients. The TENS electrode will be connected by lead wires to the Biostim M7 TENS (Biomedical Life Systems, Vista CA) unit or equivalent set at 20 HZ. The TENS unit will be turned on and stimulation slowly increased to the patient's first sensory level and then turned off.

**Open-Label:**

At visit 13, after completion of all research related activities, patients will be unblinded to treatment. Patients who were assigned to the sham arm, will be given the option to complete active PTNS therapy and receive open label treatment. If agreed, visit 13 outcome measures will subsequently be used as baseline measures to assess the effect of PTNS therapy on treatment.

**B. Study visits:**

**Screening and Consent Visit 0: Week 0**

Eligible patients that have provided voluntary written consent, will complete the enrollment questionnaires including (demographics, medical history, concomitant medications etc.) and OAB-q-SF. If a subject needs to be discontinued from antimuscarinics/beta-3 agonists, this will be discussed after consent. The subject will discontinue the use after the time of consent for  $\geq$  2 weeks and remain off throughout study participation. Patient will need to be screened after washout period to assess if patient still meets eligibility criteria. A urinalysis via urine dipstick and pregnancy test (for women of child-bearing potential) will be performed at screening. *If the urinalysis is positive for leukocytes a urine culture will be sent. Patients with a positive urine culture may be treated per standard of care by the study physician. After treatment is completed, a repeat urine will be checked. If repeat urinalysis is negative, the subject will be allowed to complete the 3-day voiding diary and study activities.* A 3-day voiding diary and instruction will be reviewed with and dispensed to the subject to return at their next scheduled visit.

Subsequent visits that require a urinalysis and are positive for leukocytes if the patient is symptomatic, a culture will be sent per the investigator's discretion.

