**Enrollment and Treatment 1: Visit 1: (within 3 weeks of visit 0  $\pm$  3 days)**

The diary will be collected and reviewed at the first scheduled treatment visit. The RN will verify the subject has remained off antimuscarinics/beta-3 agonists for at least 2 weeks and if eligibility criteria are still met (if applicable). Medication may be resumed in the event participant does not meet study eligibility criteria. After all screening activities have occurred and it has been determined that the patient meets all inclusion criteria without the presence of exclusionary criteria patients will be randomized 1:1 to active PTNS treatment or Sham treatment. A urinalysis via urine dipstick and pregnancy test (for women of child-bearing potential) will be performed. Treatment 1 will be completed at this visit. Patients will be considered enrolled in the study after randomization.

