**VI. Data Analysis Plan**

The primary outcome measure is the PGI-I score. The PGI-I will determine the patient perception of symptom improvement based on a single question. The PGI-I score given by the patient will range from 1-7, with 1 being very much better and 7 being very much worse. Scores

**Percutaneous Tibial Nerve Stimulation (PTNS) therapy for female patients suffering from  
Multiple Sclerosis**

of 1 and 2 will be considered as clinically meaningful improvement in OAB symptoms. The percent of patients with significant symptom improvement will be compared between the active and sham treatment groups using a one-WAY ANOVA test.

The secondary outcome measures include the 3-day voiding diary and the OABq-SF questionnaire. For both, baseline measures will be taken prior to first treatment and again at the completion of treatment. The change in OAB symptoms (e.g. number of daytime voids and urgency episodes) and the change in OAB symptom bother (e.g. how have your symptoms adjusted planned activities?) between baseline and at the end of treatment will be calculated for each study participants. The average change in symptom (bother) will subsequently be compared between active and sham treatment groups using two-WAY ANOVA.

Finally, patient assigned to receive sham treatment have the option to crossover into active treatment after completion of the sham portion. For patients who complete both sham and crossover studies, data from OABq-SF and 3-day voiding diary will be analyzed using a one-WAY ANOVA in which the average values of three time points (baseline, end of sham treatment, end of crossover) are compared.

As this study is a pilot study, no official power analysis was performed. The sample size was chosen based on the limitations of the budget, which was largely driven by the cost of the PTNS and sham needles. A total of 34 patients will be enrolled in the study, 17 per treatment group. The 17 patients that are randomized into the sham treatment have the option of completing the active treatment (crossover). Data (OABqSF, 3-day voiding diary, PGI-I) will continue to be collected during the crossover study and analyzed as described above.

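### For patients washed out of bladder drugs, the OABq-SF baseline is taken before washout and the diary baseline may be, so change from baseline can mix loss of drug effect with treatment effect

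*Combined protocol and SAP*

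**What the plan says.** Under Screening and Consent Visit 0 (Section B, Study visits), patients "will complete the enrollment questionnaires including (demographics, medical history, concomitant medications etc.) and OAB-q-SF". For anyone on antimuscarinics or beta-3 agonists, the same section puts the stop after that point: "The subject will discontinue the use after the time of consent for" at least 2 weeks, and the patient stays off for the rest of the study. It adds a safeguard: "Patient will need to be screened after washout period to assess if patient still meets eligibility criteria". On the diary it says: "A 3-day voiding diary and instruction will be reviewed with and dispensed to the subject to return at their next scheduled visit".

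Under Enrollment and Treatment 1 (Visit 1), the diary is collected and "The RN will verify the subject has remained off antimuscarinics/beta-3 agonists for at least 2 weeks", along with continued eligibility. Randomisation, urinalysis, pregnancy test and treatment 1 follow. No OABq-SF is listed. The visit text next names it at Visit 13.

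Baseline is defined in two places. Objectives and/or Endpoints: "Secondary outcome measures will be assessed at baseline (prior to visit 1) and at the end of treatment (visit 13"). Section VI, Data Analysis Plan: "For both, baseline measures will be taken prior to first treatment and again at the completion of treatment". Section VI compares mean change between arms. For sham patients who cross over, it also plans an ANOVA in which the "average values of three time points (baseline, end of sham treatment, end of crossover) are compared".

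Table 1 (Schedule of Events) is too damaged in the available text to confirm or exclude a repeat OABq-SF at Visit 1.

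**The concern.** A change score should compare like with like. For a patient who comes off a bladder drug, the Visit 0 form describes symptoms on the drug and the Visit 13 form describes symptoms off it. The Risks and Benefits section itself warns that frequency, urgency and leakage may rise after washout. That rise would count as worsening during the study and hide part of any improvement on PTNS. The same applies to a diary filled in soon after Visit 0, before the drug effect has gone.

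At stake are the within-arm mean changes on the secondary outcomes and the crossover contrasts that use the original baseline. A pilot meant to support a multi-institutional trial would report these changes. There is a smaller consequence for entry: the criterion of at least 4 on OAB-q question 1 at screening could be judged on the on-drug form, and no sentence says which form counts.

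**Working it through.** The plan gives no SD, effect size or power for these outcomes, so there is no figure of its own to reproduce. Two checks apply: the calendar, and an illustration of size.

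**Calendar.** Inputs: washout of at least 14 days; Visit 1 within 21 days of Visit 0, ± 3 days. Assume the drug stops on the day of Visit 0 (day 0).

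- Visit 1 can fall from day 14 (shortest washout) to day 21 + 3 = 24, which is 11 permitted days.
- Three full diary days after a 14-day washout are days 14, 15 and 16 at the earliest, so Visit 1 must be on day 17 or later.
- On days 14–16 (3 of the 11) the nurse's check is passed but a fully post-washout diary is impossible.
- From day 17 it is possible but not required. With Visit 1 on day 21, a three-day block can start on any of days 0–18 (19 blocks), and only starts on days 14–18 (5 blocks) are post-washout.

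**Size.** Let *f* be the share of patients washed out and *d* the drug effect in SDs of the change score. Neither is in the documents. Assumed ranges: *f* = 0.25–0.75, *d* = 0.3–0.5. From Section VI, n = 17 per arm.

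- Shift in mean change toward worsening = *f* × *d*.
- SD of change, allowing for the mixture = √(1 + *f*(1 − *f*)*d*²).
- Between-arm standard error = √(2/17) × that SD. With no washout effect it is √(2/17) = 0.343.
- Illustrative power for baseline versus end of crossover: paired t test, n = 17 (all sham patients cross over), two-sided 5%, assumed true improvement 0.8 SD, so mean 0.8 − *f* × *d*.

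| *f* | *d* | Shift (SD) | Mean left (SD) | SD of change | Paired power | Between-arm SE |
|---|---|---|---|---|---|---|
| none | – | 0 | 0.800 | 1.000 | 0.87 | 0.343 |
| 0.25 | 0.3 | 0.075 | 0.725 | 1.008 | 0.80 | 0.346 |
| 0.50 | 0.4 | 0.200 | 0.600 | 1.020 | 0.63 | 0.350 |
| 0.75 | 0.5 | 0.375 | 0.425 | 1.023 | 0.36 | 0.351 |

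Within these ranges the between-arm standard error is largest at *f* = 0.5, *d* = 0.5: 0.343 × √(1 + 0.25 × 0.25) = 0.354, or 3.1% above 0.343. Its expected bias is zero, because randomisation gives both arms the same expected share of washed-out patients.

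**What is not touched.** The PGI-I is not a change score from either instrument. End of sham versus end of crossover is off drug at both ends, and the Open-Label section makes Visit 13 the baseline for that phase.

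**The case against.** The strongest counter-argument is the post-washout screen. OAB-q question 1 and diary frequency are eligibility criteria, and so is being off drug for at least 2 weeks. Checking that a patient still qualifies after washout therefore most naturally means giving the form again. The diary sentence also comes after the washout and urinalysis sentences, so it could be read as dispensing once screening is complete. Marks have clearly been lost from Table 1, and a Visit 1 OABq-SF could be among them.

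This makes a repeat plausible, and that stands. It does not settle the matter. No sentence names the instrument to be repeated, ties the diary days to the washout, or says which value is baseline if there are two. Both baseline definitions accept the pre-washout form, and a repeat done at Visit 1 would arguably fail the Objectives definition, which requires a value from before that visit.

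The objections on size are also fair:

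- All the magnitudes rest on assumed inputs. At *f* = 0.10 and *d* = 0.3 the shift is only 0.03 SD and the illustrative power 0.84.
- The paired test is one contrast, not the planned ANOVA, and it is not the contrast the Open-Label section designates for the open-label effect.
- A diary on days 11–13 is already off drug, and no text says the drug effect lasts until day 14. The 5 of 19 is a count of possibilities, not a probability.

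**Conclusion.** The concern holds, for patients on antimuscarinics or beta-3 agonists at consent and for the secondary outcomes only. Followed as written, the plan compares an on-drug OABq-SF with an off-drug one, and it allows the same for the diary. Under the assumed 25–75% washed out and 0.3–0.5 SD drug effect, within-arm change and the original-baseline crossover contrasts move 0.075–0.375 SD toward worsening. If few patients are washed out, the shift is small. The primary outcome and the validity of the active-versus-sham comparison are not in question. The change should be made before enrolment, because a missed post-washout baseline cannot be recovered later. If a repeat is already intended, the change only writes it down.

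**What to change.** For patients who undergo washout:

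1. Repeat the OABq-SF after washout and before randomisation, at the post-washout screen or at Visit 1 before treatment 1.
2. Require the three baseline diary days to fall after the washout already specified and before treatment 1.
3. Define these values as the baseline in Section VI.
4. State which form decides question 1 eligibility. Using the post-washout form would match the existing post-washout screen and would mean that a low on-drug score at Visit 0 does not by itself exclude a patient.

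Align the Objectives definition, the Visit 0 and Visit 1 text, Table 1, the inclusion criterion and Section VI. Patients without washout keep the Visit 0 form as baseline. The washout rule itself does not change.

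The cost is one repeated short form for this subgroup and a few sentences of text. The drawback is a tighter schedule: if the drug stops at Visit 0, Visit 1 for these patients would need to fall on about days 17–24, which is inside the existing window.

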#### **E. Replacements**

Subjects who have been randomly assigned to receive treatment and who subsequently discontinue prematurely from the study may be replaced by another subject. The ultimate goal is to have 34 patients complete the study, 17 in each arm. If/when a subject withdraws from the study prior to completing study at visit 13, an additional subject will be enrolled. Each subject will be assigned their own unique study identification number.

Subjects who fail to satisfy inclusion and exclusion criteria at screening may be rescreened at the discretion of the PI.

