**V. Eligibility Criteria**

**Inclusion criteria:**

- Women with diagnosis for Multiple Sclerosis (CIS, RRMS, SPMS, and/or PPMS), 18 years of age or older
- A score of  $\geq 4$  on question 1 of the OAB-q symptom bother short form completed by patient at screening
- Average urinary frequency of  $\geq 8$  voids per day as recorded on initial 3-day voiding diary
- Self-reported bladder symptoms  $> 3$  months
- Discontinued antimuscarinics/beta-3 agonists for  $\geq 2$  weeks and remain off throughout study participation.
- Capable of giving informed consent
- Ambulatory and able to use toilet independently without difficulty
- Capable and willing to follow all study-related procedures
- If of childbearing age, agree to practice approved birth-control methods (oral contraceptives, condom barrier, injection, diaphragm or cervical cap, vaginal contraceptive ring, IUD, implantable contraceptive, surgical sterilization (bilateral tubal ligation), vasectomized partner(s))
- Subject agrees not to start any new treatments for urinary symptoms (medication or otherwise) during the treatment and follow-up periods.
- Subject agrees to maintain a stable dose on all current medications throughout the treatment and follow-up period.

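### After a treated screening infection the baseline diary waits for a clear urine, but no repeat of the Visit 0 OABq-SF is stated

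*Combined protocol and SAP*

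**What the plan says.** Under B. Study visits, Screening and Consent Visit 0, consented patients "will complete the enrollment questionnaires including (demographics, medical history, concomitant medications etc.) and OAB-q-SF". The same paragraph then describes the urine dipstick. A leukocyte-positive result leads to a culture, a positive culture may be treated, and the urine is checked again after treatment. Then: "If repeat urinalysis is negative, the subject will be allowed to complete the 3-day voiding diary and study activities".

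The Visit 0 OABq-SF has two uses:

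- **Entry.** V. Eligibility Criteria requires a score of at least 4 "on question 1 of the OAB-q symptom bother short form completed by patient at screening". A separate criterion requires an average of at least 8 "voids per day as recorded on initial 3-day voiding diary".
- **Baseline.** II. Objectives and/or Endpoints places the baseline of the secondary outcomes before Visit 1. VI. Data Analysis Plan computes the change in OABq-SF and diary measures from baseline to end of treatment and compares it between arms. For sham patients who cross over, it also compares the averages at baseline, end of sham and end of crossover.

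At Visit 1, "The diary will be collected and reviewed at the first scheduled treatment visit". The Visit 1 text describes randomisation, then the dipstick and pregnancy test, then Treatment 1. It does not say whether the dipstick is read before the patient is randomised.

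**The concern.** Urinary infection can produce the urgency, frequency and bother that the OABq-SF measures. By holding the diary until the urine is clear, the protocol already accepts that symptoms recorded during infection are a poor baseline. It states that safeguard for one of the two secondary instruments only.

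For a patient treated at screening, two things can follow. She may meet the question 1 threshold because of the infection. And her OABq-SF change score may include recovery from the infection, which neither PTNS nor sham produced, while her diary change score does not. The two secondary measures would then start from different clinical states in the same patient.

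**Working it through.** The plan gives no power calculation, SD or infection rate, so there is no figure of its own to reproduce. The check has two parts: the order of events, then a rough size on assumed inputs.

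**Order of events for a patient treated for a screening infection**

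| Item | When recorded | State of the urine |
|---|---|---|
| OABq-SF, including question 1 | Visit 0 | Infected |
| 3-day diary | After the negative repeat urinalysis | Clear |
| PGI-I | After treatments 4, 8 and 12, and at Visit 13 | No baseline form exists |

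The diary criterion of 8 voids per day is recorded after clearance, so it still removes some patients whose symptoms came only from the infection.

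**Inputs**

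- From the documents: 34 patients, 17 per arm, randomised 1:1.
- Assumed: share *s* of randomised patients with a treated screening infection, 10% (range 5% to 15%). Inflation *d* of the Visit 0 score, 20 points (range 10 to 30) on a 0 to 100 scale where higher is worse. SD of change, 25. Infection status independent of the rest of the change score.

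**Patients affected.** 34 × *s* = 1.7, 3.4 and 5.1 for 5%, 10% and 15%.

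**Shift from one affected patient.** Her arm's mean change moves by *d*/17: 10/17 = 0.59, 20/17 = 1.18, 30/17 = 1.76 points.

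**Randomised comparison.** The infection precedes randomisation, so the expected difference between arms is 0. The added standard error is *d* × √(2*s*(1 − *s*)/17).

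- Central: 20 × √(2 × 0.10 × 0.90/17) = 2.06
- Low: 10 × √(2 × 0.05 × 0.95/17) = 0.75
- High: 30 × √(2 × 0.15 × 0.85/17) = 3.67

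Without infection the standard error is 25 × √(2/17) = 8.57. Combined:

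- Central: √(8.57² + 2.06²) = 8.82, up 2.8%
- Low: √(8.57² + 0.75²) = 8.61, up 0.4%
- High: √(8.57² + 3.67²) = 9.33, up 8.8%

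As a cross-check, fixing the number affected at 3 of 34 and allocating 17:17 gives a chance-imbalance SD of 1.97 points for *d* = 20, close to the 2.06 above.

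**Crossover analysis.** One affected sham patient raises the baseline mean by 20/17 = 1.18 points if all 17 cross over (0.59 to 1.76), or by 20/10 = 2.0 points if 10 do (10/10 = 1.0 to 30/10 = 3.0). This makes the improvement from baseline to end of sham, and from baseline to end of crossover, look larger by that amount. The step from end of sham to end of crossover does not use the Visit 0 form and is unchanged.

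**The case against.** The strongest reply is that the protocol may already allow a repeat. The words study activities in the Visit 0 sentence could include one. Section E. Replacements says: "Subjects who fail to satisfy inclusion and exclusion criteria at screening may be rescreened at the discretion of the PI". Current urinary tract infection is an exclusion criterion, so a patient infected at screening fails screening whatever her question 1 score, and that provision can reach her. If she is also stopping bladder drugs, the re-screen after washout applies. A reader might infer that no rescreen rule covers her; the documents do not support that. What stands is narrower: rescreening under E. Replacements is discretionary, neither provision lists the instruments to be repeated, and the Visit 0 sentence names only the diary. The OABq-SF row of Table 1 cannot be read in the available text, so the schedule does not settle the question either way.

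A reader might also infer that infection goes unchecked at Visit 1, because for later urinalyses that are "positive for leukocytes if the patient is symptomatic, a culture will be sent per the investigator's discretion". That goes too far. The current-infection exclusion still has to be satisfied before randomisation, and the quality-control section calls for eligibility to be verified at each visit. At screening only the culture is required; treatment is optional there too. Requiring a culture and a repeat of both baselines at Visit 1 would be a debatable trade: it would keep washout patients off their bladder drugs for longer, and the risks section lists return of symptoms as a hazard of washout. Likewise, a positive Visit 13 urine is not left without a rule, since the one just quoted covers any later visit with a urinalysis.

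Finally, every input to the sizing is assumed. It also gives each affected patient the full inflation, although the screening culture is triggered by leukocytes and not by symptoms. That objection stands, and it argues for reading the figures as generous.

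**Conclusion.** The gap is real and minor. As written, a patient treated for a screening infection can carry an OABq-SF recorded during infection into both the question 1 entry criterion and the change-score baseline, while her diary is recorded after clearance.

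On the assumed inputs the cost is about 3% on the standard error of one secondary outcome (0.4% to 9%). It would be tempting to call this bias in favour of PTNS. The documents do not support that: the form is completed before randomisation, so infection is unrelated to arm and the expected effect on the arm difference is zero. The primary outcome is not affected, because the PGI-I has no baseline measurement and does not draw on the OABq-SF. Only the crossover analysis, which has no concurrent control, has an error with a direction, and there it flatters sham and the total change from baseline. The true size cannot be known without an infection rate. This is a cheap improvement to the wording, not a threat to the pilot's main result.

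**What to change.** Add to the Visit 0 text: when the diary is deferred for a treated screening infection, the OABq-SF is repeated after the negative urinalysis and before Visit 1, and the repeated form is used both for question 1 eligibility and as the baseline. Mark the conditional repeat in Table 1.

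In the Visit 1 text, state that the scheduled dipstick is read before randomisation, so that the current-infection exclusion can be applied to that result.

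The cost is a few sentences and one extra short form for each affected patient. Some of these patients may then fail question 1 and have to be replaced in recruitment, but this happens before randomisation and so uses no treatment needle. No new scheduled test is needed.
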